8.1.5 WASHOUT PERIOD (ONLY FOR CROSS-OVER DESIGN)

Upon completing Visit 2, the site will collect the hearing aids fitted at Visit 2, store them and send them out to subjects upon completing the 5-day washout period.

8.1.6 FIELD TEST 2 (ONLY FOR CROSS-OVER DESIGN)

Field Test 2 will be conducted the same as stated in 8.1.3. Field Test 1.

8.1.7 VISIT 3 (ONLY FOR CROSS-OVER DESIGN)

At the final session after approximately 4 weeks of total field use with a 5-day washout period after two weeks of field use, each subject returns the hearing aids from their second field use test.

Subjects are asked to report any ADEs occurring during field use.

Subjects again complete two questionnaires: the APHAB and the SSQ-12, reflecting their hearing experience aided with the Field Test 2 hearing aids. An HCP or assistant reads through the filled-out questionnaires with the subject to make sure everything is understood and filled out sufficiently.

Effectiveness is measured with QuickSIN in an unaided condition and aided with the *Vibe SF* and Silk 1X HCP fit hearing aids in a sound attenuated booth. Aided testing will be conducted double-blinded and subject is given their field test 1 and 2 devices (*Vibe SF* and Silk 1X HCP fit hearing aids) in randomized order.

REM will be conducted double-blinded, and the subject is given field test 1 and 2 devices (*Vibe SF* & Silk 1X HCP fit hearing aids) in randomized order.

The subject will be asked to fill out a 5-point Likert scale to respond to the prompt: *Based on your listening experiences regarding speech understanding, sound quality and naturalness for both products, if you could keep one pair of these hearing aids, which pair would you choose: Greatly prefer A, Somewhat Prefer A, No Preference, Somewhat Prefer B, Greatly Prefer B.*

8.2 SAFETY AND OTHER ASSESSMENTS

Stage	Intervention	Method
For the duration of the study	Secondary endpoint on device safety	
Subjects are asked repeatedly to report any adverse device effects they experience:
 
 Instruction during first Visit (Visit 1). At follow-up phone call during first field test. At Second Visit (Visit 2). At follow-up phone call during second field test. At final visit (Visit 3).

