Week 5-7
(+3 days)

Sound Quality, Speech Understanding & Satisfaction EMA Ratings
ADEs: **Vibe SF** Strategy

Visit 3
Week 8
(+7 days)
Exit**Final Assessments (completed by 12 participants)**

- APHAB aided: Field Test 2 hearing aids
- SSQ-12 aided: Field Test 2 hearing aids
- QuickSIN unaided, aided (randomized, double-blinded)
- REM aided (randomized, double blinded)
- Fitting Preference Likert scale question

Interim Analysis after 12 participants, additional 38 participants enrolled & complete up to Visit 2

Schedule of Activities (SoA)

Procedures	Screening -3 months	Enrollment/Baseline Visit 1, Week 0	Field Test 1 Week 1-2 +3 days	Study Visit 2 Week 3 +7 days	Washout Period + 2 days post Visit 2	Field Test 2 Week 4-5 + 3 days	12 subjects completed Visit 3	Study Visit 3 Day 30 + 7 day
Inclusion/Exclusion Criteria	X							
Demographic (e.g., gender)	X							
Medical history (e.g., Length of hearing loss, length of hearing aid use)	X							
Self-perceived hearing loss rating	X							
Hearing Test	X							
Informed consent	X							
Randomization		X						
APHAB unaided		X						
SSQ-12 unaided		X						
Bilateral Hearing Aid fitting:								
Silk 1X Issued, HCP fit strategy: NAL NL2 REM		(X)		(X)				
Vibe SF Hearing Aids Issued, SF strategy		(X)		(X)				
Shipment and Delivery of Field Test 2 Hearing Aids at 5 days + 2 days post Visit 2					X			
APHAB aided				X				X
SSQ-12 aided				X				X
Sound quality, speech understanding and hearing aid satisfaction EMA			X			X		
Follow-up Call: EMA data collection (+3 days Field Test 1 & 2)			X			X		
QuickSIN, unaided								X
QuickSIN, aided, hearing aid order randomized, double-blinded								X
QuickSIN, Field Test 1 device (parallel-arm design)				X*				
REM, hearing aid order randomized, double-blinded (cross-over design)								X
REM, Field Test 1 device (parallel-arm design)				X*				
Fitting Preference Likert question								X
Adverse device effect (ADE) review and evaluation		X	X	X		X		X
Complete electronic Case Report Forms (eCRFs)	X	X	X	X		X		X
Final Study Visit at Visit 3 for 28 subjects (cross-over design)								X*
Final Study Visit at Visit 2 for 38 subjects (parallel-arm design)				X*				
Final Study Visit at Visit 3 for 12 subjects (parallel-arm design)								X*
Interim Analysis: Interaction Effect Detection on 12 subjects						X		

(X): Visit 1: Device Fitting Strategy order randomly issued to subject. Visit 2: Cross Over to other Device Fitting Strategy

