Fitting (Vibe SF/HCP fit) preference reported by the subject.	
Fitting preference between the Vibe SF or HCP fit strategy.
 
Subjects will be asked to give their response on a 5-point Likert scale to the following question: Based on your listening experiences regarding speech understanding, sound quality and naturalness for both products, if you could keep one pair of these hearing aids, which would you choose?
 
Time point data collected: Cross-over Design: Visit 3
 
Parallel-arm Design: 12 Subjects: Visit 3
	Assessment of perceived hearing aid benefit should include the dimension of fitting preference of the subject.
Secondary Safety Objective		
To estimate the rate of safety when the subject is using the Vibe SF hearing aids.	
The number of adverse device effects (ADEs) in the time period when the subject is using the Vibe SF strategy hearing aids.
 
Time point data collected: Cross-over Design: Visit 1-3, Field Tests 1-2
 
Parallel-arm Design: 12 Subjects: Visit 1-3, Field Test 1-2 38 Subjects: Visit 1 and 2, Field Test 1
	Record, track and report device-related events as part of the risk management process for the SF strategy validation.

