For the subjects starting with the HCP fit strategy, an HCP fits the *Silk 1X* hearing aids bilaterally using the *Connexx* fitting software to NAL-NL2 validated prescription target, probe-mic REM and conduct fine-tuning as is standard clinical practice.

All subjects are given a user manual for the hearing aids, along with instructions by the HCP or research assistant on how to use the EMA app and study smartphone. Subjects starting with the *Silk 1X* (HCP fit strategy) will be provided counselling on the use of the *Silk 1X* hearing aids and *Signia App* (remote-control smartphone app for situation tuning).

The *EasyFit* web application guides the user through the SF procedure as well as the fine-tuning and volume control functionality. Subjects who start using the *Silk 1X* HCP fit strategy hearing aids will receive instructional material on how to use the *Signia App* for situation tuning as per standard of care.

Subjects in both groups are instructed to listen to as many listening environments as possible and enter their sound quality, speech understanding and hearing aid satisfaction ratings when randomly prompted by the clinical study smartphone, and subjects may at any time self-enter a rating. The investigational staff will practice with the subjects until they have observed that the subject is able to successfully enter their sound quality, speech understanding and hearing aid satisfaction EMA ratings without any assistance from the investigational staff.

Subjects are asked to report any ADEs occurring during field use.

8.1.3 FIELD TEST 1

All subjects wear their first pair of study hearing aids for two weeks. Since the investigation is designed as a cross-over design in order to be able to do within-subject comparisons, a two-week period was chosen to allow for acclimatization and fine-tuning but not prolong the field test to an extent where it is likely that subjects would drop out of the study or be less motivated in the second field test.

The EMA rating questions on subject's sound quality, speech understanding and hearing aid satisfaction is filled out in various listening conditions daily. The EMA consists of a short survey that is triggered randomly four times during the entire day and may also be entered at any time the subject wants to enter a rating.

The EMA survey comprises of four single/multiple choice questions (or three, if the situation does not involve speech) which are:

1. Current situation,
2. Sound quality,

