8.3.3.2 RELATIONSHIP TO STUDY INTERVENTION

All adverse events (AEs) must have their relationship to study intervention assessed by the clinician who examines and evaluates the subject based on temporal relationship and his/her clinical judgment. The degree of certainty about causality will be graded using the categories below. In a clinical trial, the study product must always be suspect.

- **Related** – The AE is known to occur with the study intervention, there is a reasonable possibility that the study intervention caused the AE, or there is a temporal relationship between the study intervention and event. Reasonable possibility means that there is evidence to suggest a causal relationship between the study intervention and the AE.
- **Not Related** – There is not a reasonable possibility that the administration of the study intervention caused the event, there is no temporal relationship between the study intervention and event onset, or an alternate etiology has been established.

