8.3.4 TIME PERIOD AND FREQUENCY FOR EVENT ASSESSMENT AND FOLLOW-UP

The occurrence of an adverse event (AE) or serious adverse event (SAE) may come to the attention of study personnel during study visits and interviews of a study subject presenting for medical care, or upon review by a study monitor.

All AEs, including local and systemic reactions not meeting the criteria for SAEs, will be captured on the appropriate case report form (CRF). Information to be collected includes event description, time of onset, clinician's assessment of severity, relationship to study product (assessed only by those with the training and authority to make a diagnosis), and time of resolution/stabilization of the event. All AEs occurring while on study must be documented appropriately regardless of relationship. All AEs will be followed to adequate resolution.

Any medical condition that is present at the time that the subject is screened will be considered as baseline and not reported as an AE. However, if the study subject's condition deteriorates at any time during the study, it will be recorded as an AE.

Further details can be found in the Study Safety Plan.

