9.4.4 SAFETY ANALYSES

It is very unlikely that any device-related adverse events (ADEs) will be reported during this NSR device study. However, those that are reported will be tabulated by severity (mild-moderate-severe), seriousness (serious or non-serious) and relatedness (related, not related).

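### Every scheduled safety contact asks only for adverse device effects although 8.3.4 requires all adverse events, and the Related and Not Related grades overlap

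*Combined protocol and SAP*

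**What the plan says.** The safety endpoint in Section 3 is "The number of adverse device effects (ADEs) in the time period when the subject is using the" Vibe SF hearing aids. It is descriptive, with no hypothesis test.

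**Collection.** The Schedule of Activities has one safety row, "Adverse device effect (ADE) review and evaluation", and no row for adverse events in general. Section 8.2 states "Subjects are asked repeatedly to report any adverse device effects they experience" and lists five contacts: Visit 1, the call in each field test, Visit 2 and Visit 3. Sections 8.1.2, 8.1.3, 8.1.4 and 8.1.7 each repeat "Subjects are asked to report any ADEs occurring during field use". The field-test call in 8.1.3 is also a reminder about ADEs, and 8.1.6 runs Field Test 2 in the same way.

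**Requirement.** Section 8.3.4 says "All AEs occurring while on study must be documented appropriately regardless of relationship". Section 8.3.1 defines an AE to include unrelated events, and an ADE as an AE related to use of the device.

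**Grading.** Section 8.3.3.2 has the examining clinician grade every AE. Related is met if, among other criteria, the event is known or reasonably possible, "or there is a temporal relationship between the study intervention and event". Not Related is met if there is no reasonable possibility, no temporal relationship, "or an alternate etiology has been established".

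**Reporting.** Sections 9.1.2 and 9.4.4 describe device-related events as very unlikely and add that "those that are reported will be tabulated by severity (mild-moderate-severe), seriousness (serious or non-serious) and relatedness (related, not related".

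**The concern.** To ask a lay subject for ADEs is to ask for a causality judgement before the event is recorded, and the plan assigns that judgement to the clinician. Headache, listening fatigue or worse hearing is easily put down to something else. A subject who does so has not been asked to mention it.

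Unprompted capture may also be weakest in the period that the endpoint counts. Under 8.1.3, staff will not answer questions about the Vibe SF device, whereas HCP-fit subjects can be called in for fine-tuning visits.

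Once an event is recorded, overlapping grades mean that two clinicians following the text could classify it differently. At stake is the only safety objective of a study whose report will support a 510(k) submission. A low ADE count would be hard to separate from incomplete ascertainment.

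**Working it through.** The plan states no figure to reproduce. The check has three parts.

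**1. Prompts against requirement.**

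| Contact | Asked for | 8.3.4 requires |
|---|---|---|
| Visit 1 (8.1.2, 8.2) | ADEs | all AEs |
| Field Test 1 call (8.1.3, 8.2) | ADEs | all AEs |
| Visit 2 (8.1.4, 8.2) | ADEs | all AEs |
| Field Test 2 call (8.1.6 via 8.1.3, 8.2) | ADEs | all AEs |
| Visit 3 (8.1.7, 8.2) | ADEs | all AEs |

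No scheduled contact asks a general AE question. The 38 parallel-arm subjects would have only the first three contacts.

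**2. Overlap of the grades in 8.3.3.2.** Let P = reasonable possibility, T = temporal relationship, A = established alternate etiology. The known-to-occur criterion is left out. Related = P or T. Not Related is tried under three readings: (i) the or-list as printed, not P or not T or A; (ii) (not P and not T) or A; (iii) not P and not T and A. R = Related only, N = Not Related only.

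| P | T | A | (i) | (ii) | (iii) |
|---|---|---|---|---|---|
| 0 | 0 | 0 | N | N | neither |
| 0 | 0 | 1 | N | N | N |
| 0 | 1 | 0 | both | R | R |
| 0 | 1 | 1 | both | both | R |
| 1 | 0 | 0 | both | R | R |
| 1 | 0 | 1 | both | both | R |
| 1 | 1 | 0 | R | R | R |
| 1 | 1 | 1 | both | both | R |

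Combinations that fit both grades: 5 of 8 under (i), 3 of 8 under (ii), 0 under (iii). Reading (iii) leaves one combination with no grade. These are logical cases, not expected frequencies. Ear pain that starts during wear and has an established other cause (T = 1, A = 1) fits both grades under (i) and (ii).

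**3. Scale of under-ascertainment, illustration only.** The documents give neither an ADE rate nor a capture fraction. Assume that 10% of 28 subjects truly have an ADE, that a fraction q of these is captured by any route, and that nobody over-attributes. Expected count = 28 × 0.10 × q; chance of observing none = (1 − 0.10q)^28.

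- q = 1: 2.8 expected; 0.90^28 = 5%
- q = 0.75: 2.1 expected; 0.925^28 = 11%
- q = 0.5: 1.4 expected; 0.95^28 = 24%

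Even with perfect capture, 0 of 28 leaves a one-sided 95% upper bound of 1 − 0.05^(1/28) = 10.1%.

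**The case against.** **The subject does not decide causality.** A reader might infer that the endpoint rests on the subject's own causality judgement. It does not. The clinician grades every recorded AE (8.3.3.2), and the Independent Medical Monitor reviews causality (10.1.5). Section 8.3.4 also lets events surface in visits, interviews and monitor review, and 8.1.3 has all field-test communication documented. This stands: the subject is a first filter only, and unrelated events are unasked rather than excluded. But neither grader can assess an event that nobody mentions.

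**Part of the detail lies elsewhere.** Section 8.3.4 refers to a Study Safety Plan, which is not among the documents. It may contain a neutral question. If so, the protocol wording still needs to be reconciled with it.

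**The text steers the grader.** Section 8.3.3.2 invokes clinical judgement and keeps the study product under suspicion, which favours Related in doubtful cases. That helps, but the text does not say which grade prevails when both definitions are met.

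**The not-related row need not be empty.** A reader might infer from 9.4.4 that it must be. A subject can report a presumed ADE that the clinician then grades Not Related. The fault is loose wording, not an impossible table. Section 9.4.8 does provide subject-level listings, but a listing is not a summary.

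**The bias has no known size.** A reader might equate the understatement with the share of events that subjects fail to recognise. That holds only if no other route captures any event and no subject over-attributes. Grading on timing alone pushes the count upward, so the net direction is also open. Much of the weakness of a zero count comes from having 28 subjects.

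**Conclusion.** The concern holds as a contradiction between the scheduled prompts and 8.3.4, together with an ambiguous relatedness scale and a loosely specified table. The prompting can understate the Vibe SF ADE count, but the documents do not support a figure; the illustration above rests on an assumed 10% rate and assumed capture fractions. The overlap follows from the printed definitions and disappears only if all three Not Related criteria are required together, which is not how the sentence reads. With both the clinician and the Medical Monitor addressing causality, the plan also does not say whose grade sets the count.

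The consequence is confined to a descriptive secondary endpoint. The change is worth making because this is the only safety objective and the remedy is cheap.

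**What to change.** - **Prompts.** In the Schedule of Activities row, 8.1.2 to 8.1.4, 8.1.7 and 8.2, replace the ADE-only request with a neutral question about any new or worsened health, ear or hearing problem since the last contact, whatever its cause. Field Test 2 follows through 8.1.6.
- **Grades.** In 8.3.3.2, define Related as a reasonable possibility of a causal link and Not Related as no such possibility. Treat timing and alternate cause as evidence for that judgement, not as stand-alone criteria. Record relatedness to device and to procedure separately, because 8.3.1 ties an ADE to use of the device. State whether the clinician's or the Medical Monitor's grade is final.
- **Tables.** In both 9.1.2 and 9.4.4, tabulate all AEs by fitting strategy in use, severity, seriousness and relatedness. Count as the endpoint only device-related AEs arising during Vibe SF use. Without that restriction, Silk 1X events would enter, since the ADE definition in 8.3.1 also covers the comparator.
- **Study Safety Plan.** Align it with the new wording.

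Cost: revised wording in the protocol and the contact scripts, with no added visit or subject. A few more minor unrelated AEs will have to be recorded and graded, which 8.3.4 already requires.

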8.3 ADVERSE EVENTS AND SERIOUS ADVERSE EVENTS

8.3.1 DEFINITION OF ADVERSE EVENTS (AE)

Adverse event, as defined according to ISO1455, means any untoward medical occurrence, unintended disease or injury, or untoward clinical signs (including abnormal laboratory findings) in subjects, users or other persons, whether or not related to the investigational medical device and whether anticipated or unanticipated.

Note 1: This definition includes events related to the investigational device or comparator.

Note 2: This definition includes events related to the procedures involved.

Note 3: For users or other persons, this definition is restricted to events related to the use of investigational medical devices or comparators.

An Adverse event related to the use of an investigational medical device is called an Adverse Device Effect. This definition includes adverse events resulting from insufficient or inadequate instructions for use, deployment, implantation, installation, or operation, or any malfunction of the investigational medical device. This definition includes any event resulting from use error or from intentional misuse of the investigational medical device. It also includes comparator if comparator is a medical device.

8.3.2 DEFINITION OF SERIOUS ADVERSE EVENTS (SAE)

A Serious Adverse event is an adverse event that led to any of the following:

- a) death,
- b) serious deterioration in the health of the subject, users, or other persons as defined by one or more of the following:
 - 1) a life-threatening illness or injury, or
 - 2) a permanent impairment of a body structure or body function including chronic disease, or
 - 3) in-patient or prolonged hospitalization, or
 - 4) medical or surgical intervention to prevent life-threatening illness or injury or permanent impairment to a body structure or a body function,
- c) fetal distress, fetal death or a congenital abnormality or birth defect including physical or mental impairment

Note: Planned hospitalization for a pre-existing condition, or a procedure required by the study, without serious deterioration in health, is not considered a SAE.

Unanticipated serious adverse device effect (USADE) is a serious adverse device effect which by its nature, incidence, severity or outcome has not been identified in the current risk assessment.

Note: Anticipated serious adverse device effect (ASADE) is an effect which by its nature, incidence, severity or outcome has been identified in the risk assessment.

8.3.3 CLASSIFICATION OF AN ADVERSE EVENT

8.3.3.1 SEVERITY OF EVENT

For adverse events (AEs) the following guidelines will be used to describe severity.

- **Mild** – Events require minimal or no treatment and do not interfere with the subject's daily activities.
- **Moderate** – Events result in a low level of inconvenience or concern with the therapeutic measures. Moderate events may cause some interference with functioning.
- **Severe** – Events interrupt a subject's usual daily activity and may require systemic drug therapy or other treatment. Severe events are usually potentially life-threatening or incapacitating. Of note, the term "severe" does not necessarily equate to "serious".]

8.3.3.2 RELATIONSHIP TO STUDY INTERVENTION

All adverse events (AEs) must have their relationship to study intervention assessed by the clinician who examines and evaluates the subject based on temporal relationship and his/her clinical judgment. The degree of certainty about causality will be graded using the categories below. In a clinical trial, the study product must always be suspect.

- **Related** – The AE is known to occur with the study intervention, there is a reasonable possibility that the study intervention caused the AE, or there is a temporal relationship between the study intervention and event. Reasonable possibility means that there is evidence to suggest a causal relationship between the study intervention and the AE.
- **Not Related** – There is not a reasonable possibility that the administration of the study intervention caused the event, there is no temporal relationship between the study intervention and event onset, or an alternate etiology has been established.

8.3.3.3 EXPECTEDNESS

The Sponsor and the independent Medical Monitor will be responsible for determining whether an adverse event (AE) is expected or unexpected. An AE will be considered unexpected if the nature, severity, or frequency of the event is not consistent with the risk information previously described for the study intervention.

